An important sampling issue for our study is whether people are married or cohabitating. Randomizing people who are cohabitating to different treatment arms could lead to cross-arm contamination, potentially diluting the treatment effects. We will prescreen patients for cohabitation/marital status based on patient residence and phone number. We will then randomly choose one member of each household to participate in the intervention. In our preliminary analysis, we excluded an additional 7,659 people using this method. Because this represents fewer people than we would have expected based on national rates of marriage among older adults, we will also screen for cohabitation when recruiting. Again, based on our preliminary analysis, there will be 38,866 remaining patients eligible for recruitment.

G. Recruitment

We will recruit a subset of those patients eligible for recruitment with a goal of obtaining complete study data from 915 patients. We will identify a set of patients for recruitment by randomly choosing a subset of approximately 10,500 patients from those who are eligible for recruitment. For the patients targeted for recruited (recruitment sample), we will send them a letter in August introducing the study and inviting them to participate. The letter will inform the respondent that they have been selected to participate in a study of the effects of providing personalized information on Medicare Part D prescription drug plans and that they will be randomized to different arms representing different ways of providing that information, that participation in the intervention will allow them to easily access information from PAMF on the prescription drugs they are currently using. The e-mail will also inform the patients that they will receive a \$50 electronic Target gift certificate at the end of the open enrollment period for participating in the study following the completion of a questionnaire. The letter will direct participants to a website (enrollment portal) where they can check if they meet the eligibility criteria and, if so, enroll in the study and provide informed consent.

The initial invitation will include a study ID that the participant will use to enter the enrollment portal. This ID will be used as their study ID throughout the study and will be used to link data from their medical records to data gathered as part of the study. The enrollment portal will have 4 functions:

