1. Eligibility verification - When patients log into the application, they will verify their name and address as well as their eligibility to participate in the study based on age, part d enrollment, and single representative from their household. (We will not exclude people from accessing the tool based on the single representative but will exclude them from data analysis). They will also identify the Part D plan in which they are currently enrolled.
2. Informed consent
3. Collect contact information - Consented participants will provide their e-mail address, using double-entry verification, and will be informed that further communication regarding the study will be by e-mail rather than by mail.
4. Pre-enrollment survey (Survey 1) - We will ask a few questions intended to provide information on individual characteristics of interest for the purpose of data analysis.

We will consider people who consent through the enrollment app as the “enrolled” population. The enrolled population will be randomly assigned to one of three arms (Treatment A, Treatment B or Control). Within 2 days after subjects enroll, we will send them by e-mail a letter that includes their study ID and information on how to access the tool, including the location of the website, when it will be available and log-in instructions. They will use the study ID to log into the website when open

enrollment begins. Shortly before and close to the end of open enrollment, we will send them another reminder with the same information.

We will provide support to study participants in the form of an e-mail address and a phone number they can call. This information will be available in our study tool, the control arm screen and the consent form. We will indicate that they will receive a response within 48 business hours.

Table 1: Recruitment Objectives

Sample Name	Category	Assumptions	Number of Study Subjects
Eligible for Recruitment	Eligible for recruitment		38,866
Recruited Sample	Chosen for mail recruitment	Derived from assumptions below	10,417
	Check for Eligibility	20% of those who contacted by mail check their eligibility	2,083
Enrolled Population	Enroll in Study	Assume 40% attrition among those who access enrollment app	1,250
Study Sample	Complete final survey	Assume 80% of those enrolling complete final survey	1,000
Objective based on sample size calculation		based on 3 arms of 305 each	915

Source: trial protocol tables google sheet – recruitment objectives

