We will identify a set of patients for recruitment by randomly choosing a subset of approximately 10,500 patients from those who are eligible for recruitment. We estimate that 20% of those contacted will choose to access the enrollment portal. Among those who access the enrollment portal, we estimate 30% attrition based on ineligibility or lack of consent. Finally, we estimate that 60% of those who enroll will complete the final survey in January. The table above identifies the effects of each these assumptions on our final sample size.

We estimate the size of the final study sample will be 1,000 people with 333 assigned to each arm. Our sample size calculations indicate that we need 305 people per arm to have adequate sample size (see detail under section “assessments”).

H. Randomization

We will randomize those who enroll in the study into two treatment arms and one control arm in which they will be directed to different on-line tools. Participants will be randomized at the time they enroll by simply assigning them sequentially to the three arms as they consent.

I. Retention

While our study period is relatively short, only lasting throughout the open enrollment period, a key issue in retention is encouraging people to participate in a survey at the end of the open enrollment

period. Study participants will receive their \$50 gift certificate from Target after completing the post open enrollment survey in January.

J. Intervention

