The study has two types of interventions. The primary intervention is access to a decision tool (Aim 1) and the second is access to a decision tool with expert recommendations (Aim 2). People who enroll in the study will be randomized to one of three arms – two treatment and one control arm. People randomized to the treatment arms will receive a one of two versions of an on-line decision tool that automatically imports information on their prescription drug use from an electronic medical record into a decision tool developed as part of the study. In Treatment Arm A (expert recommendations), the tool will provide people with a score for each plan using an algorithm for generating expert recommendations based on the individual’s prescription drug usage and the characteristics of the different plans. In Treatment Arm B (individual analysis), we will provide information on each of the characteristics underlying the expert recommendation but not the recommendation itself. In the control arm, people will receive information on how to download their prescription drug information from the electronic medical record and how to access the Medicare.gov Plan Finder tool.

The calculations underlying the calculator as well as the expert recommendations will be powered by software we have purchased from a private third party, [REDACTED]. [REDACTED] produces software that allows a user to enter electronically a set of prescription drugs and returns information on associated out-of-pocket spending and the premium for each Part D plan available to the beneficiary. [REDACTED] also provides a “score” which represents a weighted average of the person’s estimated out-of-pocket spending and premium and the plan’s consumer satisfaction rating. Our user interface will, in turn, present this information to study participants in a patient-centered way and will manipulate the information in the two study arms as described above.

Participants will not actually enroll through our calculator. Instead we will direct participants to the appropriate company website or to the Medicare website where they can enroll.

The decision tool will be available throughout the open enrollment period.

K. Assessments

The study outcomes will be based on both primary data collection and administrative data sources. The sample size was chosen to adequately power the primary study outcomes.

Table 2: Summary of Outcome Measures for Comparative Effectiveness Evaluation

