Note: Primary study outcomes are italicized and bold.

Outcome Type		Measures	Data Source
Patient Satisfaction	Aims 1 and 2	• Satisfaction with choice process	Post-enrollment survey (primary)
Plan Choice	Aims 1 and 2	• Change in Part D plan chosen	2016 plan from enrollment app and 2017 plan from post

			open enrollment survey. Also question in post enrollment survey about “did they change their plan?”
	Aims 1, and 2	
 • Indicator of enrollment in lowest cost plan* • Indicator of enrollment in expert chosen plan* 	2017 plan from post open enrollment survey and information on OOP cost from [REDACTED] collected in admin panel.
Spending on prescription drugs	Aims 1, and 2.	
 • Difference in spending between lowest cost plan and chosen plan* 	[REDACTED] information for all plans and indicator of which plan was chosen from post open enrollment survey.
	Aims 1 and 2	
 • Difference in spending between 2016 plan and 2017 plan based on initial drug list.* 
Note: this address whether they switched to a lower cost plan
	[REDACTED] information for all plans and indicator of which plan was chosen from post open enrollment survey and which plan they were initially enrolled in from enrollment app.
Choice Experience	Aims 1 and 2	
 • Decisional Conflict • Knowledge about Part D program • Sources of information used • Time spent making decision 	Post-enrollment survey
		
 • How satisfied were you with the process of choosing a plan? • Decision confidence • Decision conflict • Choice knowledge – understanding of features of chosen plan • Right amount of information • Define user monitoring outcomes 	Intervention survey

* Note that calculating these variables requires a drug list for each person. For all people, we can construct an initial drug list based on the data in the EMR. For a subset of people who we observe using the tool, we can construct a revised drug list based on their activity in the tool. All these outcomes are based on the initial drug list.

L. Data Management

See data flow chart document.

M. Study Timeline

May 31 – Large dataset of test data

June 30 – UI changes implemented

July 15 – refreshed study data available to developer

July 31 – administrative console implemented

August 1 – Invitations mailed to participant

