August 1 – October 14 – recruitment and enrollment

August 1 – website available with “coming soon” information

August 1-August 30 – complete testing and list of changes to developer

September 30 – all changes implemented

October 1 – generate dataset of all [REDACTED] information for everyone chosen for recruitment.

October 1 – October 12 – final verification of functionality

October 15 – e-mail reminder (exact date depends on when tool is refreshed with 2016 open enrollment information)

October 15 – December 7 – Open enrollment – tool available

December 8 – e-mail follow up survey

January 4 – e-mail reminder about survey

December 8 – January 15 – follow up survey open

January 16 – e-mail gift cards

2. Statistical Plan

Sample size calculations:

	Hypothesis						
Outcome	Relative to control, treatment groups will have:	Baseline rate	SD	Change	Power	N per group	Notes:

Plan switching	Higher rates of plan switching	13.6		8.704	80%	305	Kling et al find 28% of people in treatment group relative to 17% in control. Ketcham et al 2013 find relative high rates of switching among new enrollees - 33% between 2009 and 2010 and that switching rates increased over time. KFF (2103) finds 13.6 among all ages in PDP plans. Change is Kling effect of 65% change applied to KFF baseline rate.
Satisfaction with choice process	Greater satisfaction with the choice process	2.6	1.03	0.6	80%	50	Scale of 1-4 in preliminary study with 1 as very satisfied. Data represent means of medicare versus all vendus arms where medicare is the baseline.
Decisional conflict	Less decisional conflict						
Coverage	enrollment in plans that coverage current drugs more generously	368	286	74	80%	236	Based on Kling et al
Coverage (alternative)	Increase in coverage generosity from last years to this years plan	-129	588.42	-543	80%	20	Based on Fall 2015 Results

Analyses:

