For aims 1 and 2, we will compare outcomes between each treatment group and the control group, defining the study population as those who enroll in the study through the enrollment portal and are randomly assigned to a study arm. The main focus of our analyses will be the comparison of the Expert arm relative to the control arm. We will calculate differences in means and proportions using t-tests and chi-squared tests based on the type of study outcome. We will also test the expert arm relative to the treatment arm without expert recommendations to identify the independent effect of expert recommendations. We will develop unadjusted estimates of the treatment effect as well as estimates adjusting for individual characteristics from survey and administrative data.

For aim 3, we will analyze how individual characteristics affect whether people choose to participate in the trial (take up of our invitation to participate). The key study variables will include age, use of myhealthonline, and prescription drug profile.

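### The only allocation rule in the plan reads as rotation by order of consent, which is not the random assignment that the plan claims and on which its treatment comparisons rest

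*Combined protocol and SAP*

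**What the plan says.** Section H (Randomization) first says that enrollees will be randomised to two treatment arms and a control arm. It then gives the mechanism: "Participants will be randomized at the time they enroll by simply assigning them sequentially to the three arms as they consent". No other allocation mechanism appears in the documents.

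Elsewhere the plan describes allocation as random:

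- Section G, on the invitation letter: "they will be randomized to different arms representing different ways of providing that information".
- Section G, on the enrolled population: "The enrolled population will be randomly assigned to one of three arms (Treatment A, Treatment B or Control".
- Section J: "People who enroll in the study will be randomized to one of three arms".
- Statistical Plan, Analyses, on the comparisons for Aims 1 and 2: "defining the study population as those who enroll in the study through the enrollment portal and are randomly assigned to a study arm".

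Section L (Data Management) says only "See data flow chart document", and that document was not available for this review. The Study Timeline (Section M) gives "August 1 – October 14 – recruitment and enrollment" and "October 15 – December 7 – Open enrollment – tool available". The title page is dated September 23, 2016.

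**The concern.** Filling three arms in turn as people consent is systematic allocation. Once the starting arm is known, every later assignment is fixed by arrival order. The plan nevertheless calls the procedure randomisation, in the same sentence and in several other places.

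Two things are at stake. First, the analysis population is defined by random assignment, and the main comparison (expert arm against control) depends on that property. A trial run by the stated rule could not accurately be reported as randomised, and the invitation letter would have told participants something that was not so. Second, rotation offers no concealment in principle. The plan does not say who can see the running order, so a reader must take it on trust that nobody who knew it could influence who entered next. Later analysis cannot put a missing random element back.

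**Working it through.** **1. Is a chance element described for allocation?** Sections G, H and J and the Statistical Plan mention no random number generator, random list, seed, block or concealment for assigning arms. The plan does state a chance step for two other selections: one member per household (Section F) and the mailing subset of about 10,500 (Section G). For arms, the only operation given is sequential assignment in consent order.

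**2. Can the rule and the label both hold?** Under rotation, participant *k* goes to arm ((*k* − 1) mod 3) + 1. Given *k* and the starting arm, nothing is left to chance. Random assignment requires that the arm not be determined by *k*. So either the rule in Section H is wrong as written, or the description of allocation elsewhere is.

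**3. How predictable is the next assignment?** The guesser is assumed to know every earlier assignment and, for blocks, where each block starts, and to guess the arm least used so far in the block.

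- Rotation: 100%.
- Simple 1:1:1 randomisation: 1/3 = 33%.
- Permuted block of 3: (1/3 + 1/2 + 1)/3 = 61.1%. Blocks of 6 and 9 give 56.1% and 53.2%.
- Equal numbers of blocks of 3, 6 and 9, weighted by length: (3 × 61.1 + 6 × 56.1 + 9 × 53.2)/18 = 55.5%.

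The documents describe nobody who holds this knowledge. These figures describe the method and do not show that steering happened.

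**4. Does the planned sample size depend on this?** The inputs come from the sample size table: 13.6% switching in control, a change of 8.704 points (so 22.304% under treatment), and 80% power. The table states no alpha, so two-sided 5% is assumed. With pooled variance and no continuity correction:

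- n = [1.960 × √(2 × 0.17952 × 0.82048) + 0.842 × √(0.136 × 0.864 + 0.22304 × 0.77696)]² / 0.08704²
- n ≈ (1.0638 + 0.4538)² / 0.007576 ≈ 304.0, rounded up to **305**. This reproduces the plan's figure, and 3 × 305 = 915.

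The formula uses arm sizes and event rates only. Correcting the allocation rule leaves 305 unchanged.

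**5. Is there evidence of bias?** No. In 40,000 simulated trials under rotation without steering, the type I error for plan switching was 4.99%. That result is nearly automatic when outcomes are generated independently of consent order. It shows that rotation does no harm under that assumption, but it does not test the assumption.

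**6. Could people already have been assigned?** Assignment takes place at enrollment. From August 1 to September 23 is 30 + 23 = 53 days; from August 1 to October 14 is 30 + 30 + 14 = 74 days. The document is therefore dated 53 days into a 74-day window. Section G has access details e-mailed within 2 days of enrolling. If recruitment kept to the timeline, some people may already have had an arm. The document does not say.

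**7. How long a list is needed?** Table 1 gives 10,417 × 0.20 × 0.60 = 1,250 enrolled. The text of Section G uses 30% attrition, giving 10,500 × 0.20 × 0.70 = 1,470. About 1,500 slots cover both.

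**The case against.** The best defence is that the plan says repeatedly that allocation is random, including in the disputed sentence. On that view, sequential assignment could mean that each new person takes the next slot on a prepared random list, with the detail held in the data flow chart document. This has some force. The repeated wording is real textual support, and the unseen document may hold operational detail. But no list is mentioned, Section H does not refer to the flow chart, and its wording most naturally describes taking turns. Even on this reading, the plan does not say how the sequence is generated or concealed.

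A second defence is that nothing numerical changes, so this is only a reporting clarification. Invitees are a random draw, they consent for themselves on a portal, access details follow by e-mail, and assignment after consent is already planned. All of that stands and is why little bias is expected. It does not dispose of the point: a stated rule that fails to deliver a stated design property is an error as written, not a missing detail.

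A reader might infer that participants were in fact rotated, or that the treatment comparisons are biased. The documents support neither. They record no actual assignments, and they describe no route by which staff or participants could exploit the order.

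**Conclusion.** The point holds as a contradiction between the stated allocation rule and the stated design. On its natural reading, Section H specifies rotation, which is fully predictable to anyone who knows the running order. Sections G and J and the Analyses section require random assignment. A random list may have been intended but is not described.

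No bias, inflation of type I error or loss of power is claimed. The expectation of little bias assumes that consent order cannot be steered and is unrelated to outcome; the portal process makes this plausible but does not guarantee it. The sample size is unaffected: 305 per arm reproduces under an assumed two-sided 5% test. What is affected is whether the comparisons can be described as randomised, so the rule needs correcting, not just rewording for style. The tools open only on October 15, so people not yet assigned can still be randomised before any tool is used. New wording cannot do that after the fact for anyone already allocated by rotation.

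**What to change.** In Section H, replace the allocation sentence with text to this effect: participants are assigned 1:1:1 by a computer-generated random sequence (simple, or permuted blocks of varied size), concealed from participants and study staff, with each assignment released only after consent. Either type of sequence is acceptable. If a random list was already in use, say so and state how it was generated and concealed.

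The rest depends on what has already happened:

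- **Nobody assigned by rotation:** the wording in Sections G and J and in the Analyses section can stand.
- **Some assigned by rotation:** report how many and when; describe that part as systematic (quasi-random) allocation; amend the population definition in the Analyses section to match; tabulate baseline characteristics by arm (age, myhealthonline use, drug profile, 2016 plan and Survey 1 items); and report the main comparison with and without those participants.

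The cost is one list of about 1,500 slots. Arm assignment is not among the four portal functions listed in Section G, so a small look-up step may be needed; the documents do not say. No extra participants are required.

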In this study, we will test the effectiveness of two versions of a web-based tool to help people choose among Part D plans (Treatments A and B) relative to each other and relative to standard care (Control). Both treatment arms will incorporate simplified design and automated importation of an individual's drugs relative to standard care. The treatment arms will vary based on whether they provide expert guidance on recommended plans. In the control arm, study participants will be directed to the existing, publicly available Medicare.gov website and will receive instructions on how to download their drugs from the Palo Alto Medical Foundation (PAMF) patient-facing EMR (myhealthonline). Our study sample will include PAMF patients who were enrolled in Part D plans during the 2016 enrollment period. Prior to the 2017 open enrollment period (October 15 to December 7, 2016), we will invite a subset of PAMF patients enrolled in Part D plan to participate in a study examining the effectiveness of decision tools that provide personalized information on the financial implications of enrolling in different Part D plans.

For aims 1 and 2, the *primary study outcomes* will be:

- 1) Plan switching
- 2) Change in generosity of coverage of prescription drugs

- 3) Satisfaction with the choice process
- 4) Decisional conflict

Secondary study outcomes for aims 1 and 2

- 5) Enrollment in an expert-recommended plan
- 6) Difficulty choosing a plan
- 7) Confidence in choosing a plan
- 8) How much do you like the plan you chose
- 9) Satisfaction with chosen plan (people found this difficult)
- 10) Knowledge of the Medicare Part D prescription drug benefit?

For aim 3, we will analyze how the following patient characteristics influence enrollment in the trial and take-up of the treatment among those randomized to the treatment arm:

- 1) Prescription drug profile
- 2) Age
- 3) Use of myhealthonline

We will measure the primary study outcomes using a combination of administrative data and a post open enrollment survey administered to all study participants. We will also collect information on individual characteristics at the time of enrollment in the study and implement a survey examining use of the intervention tool to assess patient experience at the time of use.

D. Background

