In our ethnographic study, older adults also expressed interest in having additional support, often indicating they would like the help of an expert, such as an insurance broker or other type of knowledgeable individuals.

Our study is based on the hypothesis that these barriers create switching costs for beneficiaries and that removing these barriers would lower switching costs making beneficiaries more likely to evaluate their alternatives and to enroll in plans that provide better coverage for the drugs they are likely to use. We also hypothesize that reducing switching costs, particularly by providing expert recommendations, will reduce decisional conflict and create greater satisfaction with the choice process.

While the tool we have designed in partnership with patient stakeholders is easier to use than the Medicare.gov website, it provides less detail on how the different plans cover particular types of drugs. In our qualitative work examining the use of the first version of our tool, we found that its simplicity was more attractive to some people than others. Thus, we will examine particular characteristics of individuals including numeracy, "do-it-yourselfness", and satisficer/maximizer behavior influence how people evaluate the decision process in the different tools.

A final issue in this context is whether simply providing access to web-based decision support tools is likely to assist the types of people who experience the greatest difficulty in decision-making. We will examine the take-up of decision support in this setting to determine how well targeted it is by analyzing who chooses to enroll in our trial and among those who enroll, who uses the study intervention.

E. Participants

Our study population will include PAMF patients aged 66 to 85 who were enrolled in Part D coverage during 2016. We plan to have a final study sample of at least 915 people with complete data on study outcomes.

F. Screening

We will prescreen patients using administrative data to identify potential study participants based on whether they are enrolled in Medicare, their age (66-85), whether they live in the primary PAMF service area (county=Santa Clara, San Mateo, Santa Cruz, and Alameda), and whether they have active medication orders in the PAMF EMR. We will also exclude patients enrolled in MediCal or a Medicare Advantage plan in 2016. In preliminary analyses, we have identified 46,525 PAMF patients who meet these criteria.

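### Table 2 lists time-of-use survey items, including the only listed source for decision confidence, as comparative outcomes, although that survey very likely reaches only participants who log in or use a tool

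*Combined protocol and SAP*

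**What the plan says.** Section 1.K titles the table "Table 2: Summary of Outcome Measures for Comparative Effectiveness Evaluation". Its final block, under Choice Experience, gives the intervention survey as the data source for "How satisfied were you with the process of choosing a plan", decision confidence, decision conflict, choice knowledge and the right amount of information.

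Section 1.C describes two surveys after enrolment. One is "a post open enrollment survey administered to all study participants". For the other, the investigators will "implement a survey examining use of the intervention tool to assess patient experience at the time of use". The same section names confidence in choosing a plan as a secondary outcome for aims 1 and 2. Table 2 lists confidence only under the intervention survey.

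The plan expects tool use to be partial. Section 1.D asks, "among those who enroll, who uses the study intervention", and the footnote to Table 2 begins a sentence with "For a subset of people who we observe using the tool". Control participants are told "how to access the Medicare.gov Plan Finder tool" (section 1.J).

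For aims 1 and 2 the Analyses section of the Statistical Plan says "we will compare outcomes between each treatment group and the control group", and defines the study population as everyone who enrols and is randomised. It does not mention the intervention survey, non-users, or how controls would supply its items.

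**The concern.** The declared population and the data source do not match. Arms are to be compared in all randomised participants, but a survey taken at the time of use can be answered only by people who use something. Use comes after randomisation and may depend on the arm. A control participant sent to an outside website may supply no answer, or may answer only after opening the study's control screen. The respondents being compared could therefore differ in ways that have nothing to do with the tool, and that difference would be read as a tool effect.

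The outcome most exposed is decision confidence, because the plan lists no all-participant source for it. Satisfaction and decisional conflict each have a version in the all-participant survey, but the plan does not say that only this version supports comparisons between arms.

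**Working it through.** **The plan's own figures.** The plan gives no number for the intervention survey. The nearest is the sample-size row for satisfaction: change 0.6, SD 1.03, power 80%, 50 per group. At an assumed two-sided alpha of 0.05, the normal formula gives 2 × (1.960 + 0.842)² × (1.03/0.6)² = 46.3, so 47; the t-test version gives 47.24, so 48. That is close to the stated 50. The plan-switching row (13.6% versus 22.304%) reproduces its 305 per group exactly.

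**Who answers what.**

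| Item | Source in Table 2 | Who can answer |
|---|---|---|
| Satisfaction, decisional conflict (primary) | Post open enrollment survey | All participants |
| Satisfaction, decision conflict (second version) | Intervention survey | Those present at time of use |
| Decision confidence (secondary outcome) | Intervention survey only | Those present at time of use |
| Choice knowledge (features of the chosen plan) | Intervention survey only | Those present at time of use |
| Part D programme knowledge (a different measure) | Post open enrollment survey | All participants |

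**Size of the bias, by assumption.** Suppose there is no true effect, willingness to respond is a normal score with correlation r to the outcome, and the top fraction s of each arm answers. The respondents' mean then shifts by r × φ(z_s)/s SD, where z_s cuts off the top fraction s.

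- s = 0.5: φ(0)/0.5 = 0.3989/0.5 = 0.798.
- s = 0.8: φ(−0.842)/0.8 = 0.2800/0.8 = 0.350.
- Spurious difference between arms: r × (0.798 − 0.350) = 0.448r. This is 0.09 SD at r = 0.2 and 0.18 SD at r = 0.4.
- With 305 per arm there are about 152 and 244 respondents, so SE = √(1/152 + 1/244) = 0.103 SD.
- Difference divided by SE: 0.87 and 1.73. The chance of a two-sided p below 0.05 is about 14% and 41%, instead of 5%.

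**A second scenario.** Take the 1,250 enrolled in Table 1 (about 417 per arm), with 60% answering in one arm (250) and 30% in the other (125), and SD 1.03. The multipliers are 0.644 and 1.159. The spurious difference is 1.03 × r × 0.515, or 0.05, 0.16 and 0.27 scale points for r = 0.1, 0.3 and 0.5. The false-positive rates are about 8%, 29% and 65%.

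**Equal take-up.** With the same s and the same r in both arms, the shifts cancel and the rate stays at 5%.

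**Power is not the issue.** At 20% take-up (about 83 per arm), power for a difference of 0.6 is still about 96%.

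**The case against.** Several points on the other side have force.

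- No section lists the recipients of the intervention survey. Section 1.G mentions a control arm screen, so controls who log in may be surveyed. This stands: users-only is a strong inference, not a stated fact. But controls who log in are also a subset formed after randomisation.
- The Analyses rule is limited to aims 1 and 2, and the intervention-survey block is the only one in Table 2 without an aims label. The block also contains an unfinished placeholder about user monitoring. It may be meant as descriptive. Against this, the table's title says otherwise, and confidence is named elsewhere as a secondary outcome for those aims.
- Table 2 does not list every secondary outcome (difficulty choosing a plan is absent), so a confidence item may exist in the post open enrollment survey without being listed. That is possible, and the plan should say so.
- A reader might infer that two primary outcomes are compromised, or that a more favourable version could replace them. The documents do not support this: Table 2 sources both primary outcomes from the all-participant survey, and nothing suggests substitution. The direction of any bias is also unknown.
- A reader might set the users' shift against an unselected group (0.07 to 0.32 SD) beside the 0.23 SD detectable with 305 per arm. That comparison does not fit. If no controls answer, there is no test; if some answer, only the difference in selection matters. With 50 to 80% responding, there are also fewer than 305 per arm.
- Comparison of arms A and B is less exposed. If log-in precedes sight of the version and completion does not depend on it, the respondents may be alike. The plan neither states nor checks this.

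**Conclusion.** The point holds in limited form. As written, the plan puts decision confidence, and second versions of satisfaction and decisional conflict, into an arm comparison whose data very likely come from subsets formed after randomisation. The primary outcomes are unaffected.

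The size cannot be fixed from the documents, since no take-up rate is given. It ranges from zero, with equal take-up and selection, to about 0.09 to 0.18 SD under 50% versus 80% response and a correlation of 0.2 to 0.4, with a false-positive rate of roughly 14 to 41%. These figures also assume a normal selection model, a two-sided alpha of 0.05 and no true effect. The problem is clearest for treatment versus control and weaker for A versus B.

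**What to change.** 1. In Table 2 and the Analyses section, state that treatment-versus-control comparisons of satisfaction, decisional conflict, confidence and knowledge use the post open enrollment survey sent to all participants.
2. Name that survey as the source for confidence. Add the confidence item if it is not already there, and the choice-knowledge item if that is to be compared.
3. State who receives the intervention survey in each arm and when, and label its items as descriptive of users.
4. If A and B are compared on those items, report log-in and response proportions by arm and state that the comparison is conditional on use.

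The cost is a few sentences, a relabelled table block and one or two survey items. The downside is that the time-of-use measures, which are closest to the experience itself, lose comparative status.
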